7.5.7.2 Vaginal Samples for Microbiota Analyses

Vaginal samples should be collected during the speculum exam. Samples will be obtained using a Dacron swab. Remove study swab from kit and unscrew cap from red top tube. Insert swab into the vaginal canal and gently brush the swab against the surface of the vaginal wall. Rotate the swab clockwise approximately 3 times during collection to ensure adequate cell sampling. Remove swab and place into empty tube. Break off the swab shaft at the score even with the top of the tube. Align the shaft with the hole inside the tube cap and push down tightly over the shaft, sealing the tube. Screw red cap on. Repeat process with second swab. Refrigerate at 4°C and transfer to -20°C as soon as possible. Complete the sample collection log to indicate date and time swabs are transferred to refrigerator and/or freezer.

7.5.7.3 Concomitant Medications and Exposures

Concomitant medications for the purpose of this study are to include: antiretroviral therapy, other vaccines;; exposures will include: use of drugs of addiction, tobacco, and alcohol.

At each visit, subjects will be asked about their medication usage/exposures. Information collected as part of the original CTN 236 will be reviewed with the subject and any changes to medications will be documented. Information to be collected is to include: name of 'medication' (generic name or trade name for combination medications), medical indication, and total daily dose, route, start and

stop dates. PRN medications may be listed as PRN for total daily dose.

If a subject is on and off a treatment throughout the study, please ensure that the start and stop date indicate the time the subject was on and off treatment. Additionally if the dosages change a stop date should be entered for the previous dosage and a new entry made for the start of the new dosage.

For exposure to drugs of addiction, tobacco, and alcohol, use the most basic description, for example, THC, heroin, cocaine etc., tobacco, ETOH. For route, indicate whether smoked, snorted, injected, oral etc. For frequency, have subject estimate usage per day, week, or month.

7.5.7.4 Lower Urinary Tract Symptoms Survey

The objective of this survey is to further investigate the prevalence and impact of lower urinary tract symptoms in cohort participants above the age of 18. This survey is a one-time cross sectional measure comprised of 14 questions, to be administered at one study visit per participant; questions may be answered at any of the 6 possible study visits and will take 10 – 15 minutes to complete.

The survey is comprised of 14 questions and includes two validated instruments.⁸⁵ The Urogenital Distress Inventory 6 (UDI-6) asks questions about certain bladder symptoms and how much participants are bothered by them. The Urinary Incontinence Questionnaire 7 (UIQ-7), ask questions about how much these symptoms affect participants' activities of daily living. This study questionnaire concludes with one supplementary question regarding prevalence of urinary tract infections in the past year. Inclusion of this survey will provide a greater understanding of gynaecological health in this cohort and speak to any relation between HPV infection and urogenital distress.

8.0 MANAGEMENT OF CERVICAL CYTOLOGIC ABNORMALITIES

All participants (except those pre-menarchal and not yet sexually active) will undergo clinical standardized Pap smear testing as per local site standards. Cytologic abnormalities will be managed according to local algorithms. Management of cervical cytologic abnormalities will be decided by the Site Investigator and may be based on the clinical standardized Pap smear or study cervical cytologies when available. It is suggested to manage abnormal results based on the higher grade of dysplasia.

Participants who have high grade or persistent low grade changes will be referred for follow-up evaluation by colposcopists involved with local HIV treatment centres. After obtaining consent to release medical records, all colposcopic, colpophotographic and histopathologic (biopsy) results will be added to the study record; slides from biopsies will be requested by the BC Cancer Agency for central confirmation of histopathologic diagnoses. Invasive cancers diagnosed during the study will be carefully documented and recorded once local, appropriate clinical management is provided. As in previous multicentre studies of high risk HIV positive women, we acknowledge variation in local colposcopic and treatment algorithms and anticipate imperfect compliance with referral for colposcopy; similarly, cervical disease endpoints (squamous intraepithelial neoplasia or dysplasia) in this study are cytologically and/or histologically defined as appropriate. Histopathology will be reported as cervical intraepithelial neoplasia grades, 1, 2 or 3 (CIN 1, 2 or 3), or carcinoma in situ.

9.0 SERIOUS ADVERSE EVENTS

The investigator is responsible for documentation and reporting of any Serious Adverse Event that results in death.

1. Reporting/ Time Period

All SAEs resulting in death occurring during the study must be recorded and reported to the Study Coordinating Centre whether or not they are considered vaccine-related. Sites should continue to use the SAE reporting forms utilized in CTN236.

SAE reports will be faxed to [name] at the **Study Coordinating Centre within 24 hours of discovery or notification to the study centre of an SAE resulting in death and within 48 hours of discovery to the Study Data Management Centre (CTN)**. The Study Coordinating Centre will promptly notify Health Canada as appropriate. Site investigators are obligated to notify their REB as per local reporting requirements.

SAE Notification:
[name] (fax#) [contact] (24 hours)
AND CTN (fax#) [contact] (48 hours)

The Study Coordinating Centre will acknowledge receipt of the faxed SAE form.

Site Investigators should also report SAEs to their provincial adverse event reporting centre as would occur when administering any routine licensed vaccine.

10.0 PREGNANCY

All pelvic examinations, including Pap testing and study sampling will be continue during pregnancy; however, an Ayre spatula will be used to collect cervical samples in place of the cytobroom until 3 months post resolution of the pregnancy.

11.0 SUBJECT COMPLETION AND WITHDRAWAL

Investigators or their delegates will attempt to contact those study subjects who do not return for study visits. Study personnel will make at least three attempts to contact the subject using various communication means. Each attempt should be documented in the subject source documents.

A subject completing three annual visits up to and including Month 96/Visit 13 will be considered to have completed the study.

Withdrawals will not be replaced. All withdrawals will be documented including the date of the withdrawal and the reason.

12.0 LABORATORY METHODS AND ANALYSES

Please consult the Research Laboratory Manual for detailed information on the requirements for supplies, collection, and processing, and shipping of laboratory specimens.

Blood Testing

Whole blood by venous route is to be collected observing aseptic conditions into one 10 mL red top Serum Vacutainer (non-heparinized, non-EDTA, non-serum separator) tube. Specimens should be placed upright and allowed to clot for 30 to 60 minutes. After the sample has clotted it should then be refrigerated at 2-8 degrees Celsius until centrifuged. Samples are to be centrifuged within 24 hours of collection and according to manufacturer's specification to allow for complete separation of serum. Serum is to be aliquoted using a plastic pipette into 3 cryovials, each containing a minimum of 1.0 mL and then frozen between -60 and -80 degrees Celsius at the investigative site until recalled by the Study Coordinating Centre. Samples will then be shipped frozen to the Coordinating Laboratory for serum samples.

The Coordinating Laboratory will arrange for transportation of the samples to the individual laboratories performing serotesting, specifically, 1) BC Centre for Disease Control, Virology research laboratory, Vancouver, BC, and 2) Merck & Co., Wayne, Pennsylvania and 3) to remain at the BC Women's Research Laboratory at BC Women's Hospital & Health Centre.

12.1.1 HPV Serotesting

Each serum sample will be divided into 3 aliquots with one going to the BCCDC Virology research laboratory, Vancouver, BC, the second being sent to the Merck laboratory for in house assay assessments, and the third being sent to the BC Women's Research Laboratory for storage. The Merck laboratory will be conducting the immune assays on the same platform as those performed for the pre-licensure published antibody.

12.1.2 Merck laboratory Serotesting Methods

Serum anti-HPV 6, 11, 16, and 18 immunoglobulin levels will be measured using a competitive Luminex immunoassay (cLIA), and reported in arbitrary units (milli-Merck Units per millilitre or mMU/ml) relative to the standard curves generated for each individual HPV type.⁸⁶ The HPV cLIA uses yeast-derived HPV L1 6, 11, 16 and 18 VLPs that have been covalently conjugated to Luminex microspheres. The type specific HPV-VLP antibody responses are associated with specific Luminex microspheres that are identified by their distinct fluorescent dye spectral properties. Antibody titers are determined in a competitive format, where known, with type-specific labeled neutralizing antibodies for each type competing with patient serum antibodies for binding to conformation-sensitive neutralizing epitopes on the VLPs. For each HPV type, relative inhibition is compared to a pooled standard reference serum. Seropositivity will be defined in this assay as > 20 mMU/ml for HPV 6, 16 mMU/ml for type 11, 20 mMU/ml for 16 and 24 mMU/ml for 18. Of note, lower limits of detection for this assay are 8.0, 8.0, 12.0, and 8.0 mMU/ml for 6, 11, 16 and 18 respectively.⁶⁷

12.1.3 HSV2 Serology Testing

Samples will be sent to the BCCDC Virology research laboratory, Vancouver, BC for analysis. The HerpeSelect ELISA (Focus Technologies) will be used but will employ a high cutoff index value of 3.5, which has been shown to offer improved specificity in the setting of HIV co-infection.^{87,88,89} Previously stored blood will be pulled as per protocol for baseline testing and at each study visit, participants will have serum stored for batched testing of HSV type-specific antibody. After baseline determination of serostatus for all participants, follow-up testing will be performed only on previously seronegative participants to assess for interval seroconversion.

13.0 Genital sampling

All PreservCyt samples will be sent monthly by the local sites to the Coordinating Laboratory for Cytology/HPV DNA. Samples will be re-suspended in the Preservcyt and a 4 ml aliquot will be taken and sent to the [name] Laboratory for analysis of HPV DNA. The remainder of the sample will be sent to the Cervical Cancer Screening Laboratory of BC for cervical cytology.

1. HPV DNA testing – [name] Laboratory

The 4 ml endocervical samples in PreservCyt will be centrifugation at 13000xg for 15 min at 22°C, the supernatant will be discarded, the cell pellet will be left to dry and re-suspended in 300 µl of 20 mM Tris buffer, pH 8.3.^{63,64} DNA will be purified with Master pure.⁶⁵ β-globin and HPV DNA amplification and typing. Extracted DNA will be tested in batches for β-globin with PC04 and GH20 to screen for inhibitors or inadequate quantities of cellular DNA and for HPV DNA with previously described PGMY primers.^{66,67} Samples negative for β-globin are considered

inadequate. PCR L1 consensus tests are well standardized and have been validated on large numbers of clinical samples, as reviewed by members of this team.^{68,69} HPV DNA will be first amplified with PGMY09-PGMY11 and typed with the quality-controlled Linear array assay commercialized by Roche Molecular Systems.^{66,67,70-73} This specific PCR assay reliably detects 10 HPV DNA copies.^{66,71} This test permits testing and typing for 37 genital types of HPV (6, 11, 16, 18, 26, 31, 33, 35, 39, 40, 42, 45, 51-59, 61, 62, 64, 66-73, 81, 82, 83, 84, 89 and IS39 (a subtype of HPV 82)). The genotypes relevant for this proposal including 6, 11, 16 and 18 are all detected by these specific PCR protocols. The [name] laboratory has extensive experience with PCR for HPV detection.^{66-68,70-74,74-76,78-80,82,83} and has participated in the evaluation and validation of the Linear array and PGMY09-PGMY11 primers.^{66,67,70,71,83} Weak (10 HPV18 DNA copies), and strong positive HPV controls, will be included in each amplification run as internal control and precautions to avoid contamination will be in place at all times.^{68,74,76,78,80,82}

2. **Cervical Cytology – Cervical Cancer Screening Laboratory of BC**

The PreservCyt vial will be processed for cytologic evaluation following the ThinPrep protocol (Cytac Incorporated). Slides will be read by cytotechnologists at the Cervical Cancer Screening Laboratory (CCSL) of BC. Reporting rules for normal and abnormal results will be the same as for routine specimens processed at the CCSL, a facility that processes all cervical smears performed in British Columbia (up to 600,000 per year). Standard reporting of Pap smears will be according to the Bethesda criteria e.g. low grade and high grade squamous intraepithelial neoplasia (SILs)

3. **Vaginal Microbiota Analyses – [name] Lab, University of Saskatchewan**

Vaginal samples will be collected for microbiome analysis as per the VOGUE Emerging Team Grant protocol (CIHR FRN 108030; PI [name]). Samples will be transported to the [name] laboratory at the University of Saskatchewan, where total DNA will be extracted from vaginal swabs using the MagMAX magnetic DNA binding platform (Applied Biosystems). Chaperonin 60 (cpn60) amplicons¹³⁰ will be then prepared as previously described utilizing multiplexed ID sequences (MID) to pool samples during sequencing.⁹⁰ Sequencing will be performed on the Roche GS Junior pyrosequencer in the [name] lab. Raw sequence data will be processed initially using the standard on-rig software tools for quality control and filtering. Quality filter-passed read data will then be analyzed using the mPUMA bioinformatics pipeline developed by the [name] lab.⁹¹

14.0 **TRANSPORTATION OF LABORATORY SAMPLES**

All shipments of serum samples and vaginal microbiota swabs are to be shipped frozen and prepared by qualified individuals ensuring that all shipments are packed and shipped according to IATA regulations and are to be packed using dry ice.

All shipments of liquid based cytology are to be shipped ambient and prepared by qualified individuals ensuring that all shipments are packed and shipped according to IATA regulations.

All samples are to be clearly labeled with subjects' 5 digit PID#, date of collection, and visit month.

All shipments must have an accompanying biological shipment listing, with a copy being retained at the site. A biological shipment listing template will be provided to the sites by the Study Coordinating Centre.

Prior to the shipment of any samples, the sites must inform the Study Coordinating Centre regarding the date of shipment to ensure that there is someone at the Coordinating Laboratory to receive the shipment. Confirmation must be received from the Study Coordinating Centre prior to the shipment of any samples. Sites should plan to ship Monday through Wednesday to ensure that samples arrive within 72 hours of packaging to ensure that thawing does not occur before processing.

The Coordinating Laboratories will arrange for shipment of all samples (serum, PreservCyt, microbiota swabs) to the individual laboratories performing the analysis/testing.

15.0 DATA SAFETY MONITORING BOARD/COMMITTEE

The established CTN data safety monitoring board (DSMB) will be used for this study with additional representation by pediatrics and gynecology-oncology. The DSMB will provide oversight and monitoring of the conduct of the study to ensure the safety of the subjects. Additionally, the DSMB will ensure the validity and integrity of the study data. The DSMB meets twice a year.

16.0 STATISTICAL ANALYSIS

1. Statistical Analysis Plan

Demographics: Characteristics of the study population will be described with frequencies and proportions for categorical variables, means and standard deviations for normally distributed continuous variables and medians and interquartile ranges for skewed continuous variables.

2. Primary Analysis

For each of the four vaccine containing HPV types, antibody response will be summarized using GMT's calculated for age specific groups within the HIV-positive cohort. Specific age groupings have been chosen to permit age matched HIV comparisons.

- a) Antibody response for subjects aged 9-13 and those aged 16-26 will be compared to the individual patient level data from an HIV-negative cohort 86 using Wilcoxon rank-sum tests. The age adjusted fold-difference in GMT

between HIV-positive and HIV-negative populations will be calculated using generalized linear models. For women over age 26, the type specific HPV GMT will be compared to GMTs in the published literature using a sign test.

- b) Within the HIV-positive cohort, predictors of decline from peak antibody response among HIV-positive girls and women will be determined using generalized linear models. Potential covariates to be considered in these models are age, HSV-2 status, substance use, CD4 count, HIV viral load and antiretroviral status at the time of first vaccination, and CD4 nadir.
- c) Longitudinal analyses will be conducted to describe the effect of HIV on antibody response at the visits at 36, 48, 60, 72, 84, and 96 months post first vaccine dose. Generalized estimating equation (GEE) models with a unity link will be used to adjust for correlation among repeat observations within study participants. Individual level data on HIV-negative girls and young women will be available at 36, 48, 60, 72, 84 and 96 months post first vaccine dose. After adjusting for age, an interaction between HIV and time since first dose will be included in the model to test for a difference in the degree of waning of response in addition to the strength of the initial response. GEE models will also be fit for the HIV-positive girls and women alone to examine the associations.
- d) Predictors of HPV antibody seroresponse in our study population will be identified using logistic regression. This analysis is considered to be of vital importance as other vaccines have been shown to not be effective in subgroups of HIV positive individuals and could permit targeting of the proper population allowing for cost-effective use of this vaccine. The primary predictor of interest is CD4 count and justification for this is based on hepatitis B vaccination data described above. The secondary predictors of interest will include the variables: age, presence and number of strains of HPV, HIV viral load, use of HAART, use of injection drugs, and ethnicity. These predictors were chosen as ones that make the most clinical sense for potent impact on vaccine antibody response.

3. **Exploratory Analyses**

HSV analyses will employ linear or logistic regression models as appropriate, with HSV-2 serostatus as a time- updated primary predictor variable. To address these issues, we will quantify the impact of both incident (acquired within the past year) and prevalent (present at the time of diagnosis) HSV-2 co-infection on each of the primary HPV-related outcomes as described in preceding section (GMT, breakthrough HPV infections, genital tract dysplasia, and external genital warts).

Vaginal Microbiota Analysis. The output of the bioinformatics pipeline, including inventory of unique operational taxonomic unit (OTU) sequences, their taxonomic lineage and abundance, will be used to visualize and characterize the vaginal microbiota. Using various community-level analyses available as packages in R: 133

notably the BiodiversityR, 134 vegan, 135 and ALDeX2136 packages, we will apply statistical and graphical techniques to identify patterns of bacterial diversity that are associated with HPV infection and disease. Specifically, we will use compositional analysis as implemented in ALDeX2 to test for relationships between specific bacterial taxa and HPV infection and cervical dysplasia in addition to other clinical variables at each time point. Taxa thus identified will be examined for changes in relative abundance across time using mixed-effects models to control for multiple measures on each subject, and comparing to HPV infection status, HPV type and other clinical and HIV correlates. We will also use hierarchical clustering methods to determine if the bacterial communities form identifiable and robust clusters, with particular species occurring more often together. We can then test if these clusters are associated with HPV infection, burden of infection (single vs. multiple types) and evidence of cervical disease using standard statistical tests such as logistic regression and ANOVA. Finally, we will use mixed-effects models to test for changes in bacterial diversity and species richness that are associated with HPV infection, burden of infection (i.e. infection with multiple HPV types) and evidence of cervical disease while controlling for repeated measures on each subject.

HIV and Lower Urinary Tract Symptoms Analysis. Descriptive statistics will be used for baseline patient characteristics. Logistic regression analysis will be performed to determine the effect of: severity of HIV (CD4 count, viral load, AIDS criteria met), current HIV medications, time since HIV diagnosis, and vaginal microbiome on lower urinary tract symptoms, while also considering the effects of age, parity, ethnicity, sexual practices (from various questions in the HPV in HIV questionnaire), history of STI, history of UTI, smoking status, alcohol use, drug use.

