The two currently licensed vaccines designed to prevent HPV infection, have been tested in large clinical trials. There is a bivalent vaccine against HPV 16 and 18 (GlaxoSmithKline, GSK) and a quadrivalent vaccine against HPV 6, 11, 16 and 18 (Merck). In addition, a 9-valent vaccine is currently being investigated in large scale clinical trials, with positive safety, immunogenicity and efficacy data under review by the FDA. These vaccines are produced as virus-like particles (VLP's) based on the L1 capsid protein gene of the virus inserted in insect or yeast vectors. These proteins self-assemble into protein shells with identical configuration to the native virus, but without DNA, and so are deemed subunit, protein vaccines. Safety, efficacy, and immunogenicity data on these vaccines in HIV-negative populations of young women are based on clinical trials conducted by GSK and Merck, respectively, with some follow up post-licensure trials now in progress. Both have shown remarkable safety profiles in otherwise healthy young HIV-negative women, with limited local injection site reactions as the primary side-effect and no evidence for differences in serious adverse events between vaccine and placebo arms.⁶⁵

Immunogenicity to the quadrivalent vaccine has been well studied in HIV-negative populations, showing that anti-HPV 6, 11, 16 and 18 geometric mean titers (GMT) were highest at month 7 (1 month following the final dose 3). Anti-HPV GMT's declined thereafter but reached a plateau at month 24 and remained stable through 5 years.^{66,67,68} In the original immunogenicity study by Villa et al.,⁶⁷ 100% of the subjects who were antibody negative to the relevant HPV type at baseline had a detectable antibody response at month 7 to HPV 6, 11, 16 and 18 respectively. These levels were 10-to 10⁴-fold higher than natural antibody levels in placebo recipients who were vaccine type positive at baseline.

8. **HPV vaccine implementation**

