Our study group was one of the first groups globally to study one of these vaccines in HIV-positive, immune compromised populations. As the qHPV vaccine GARDASIL™ (Merck), which contains subtypes 6 and 11 (responsible for 90% of genital warts) and subtypes 16 and 18 (responsible for 70% of cervical cancer) was the first to be licensed and available in Canada for post-licensure studies, we engaged with Merck to permit an initial study of the safety and immunogenicity of this vaccine in a cohort of HIV-positive girls and women. Data from this cohort has

provided valuable information about the health of Canadian women and girls living with HIV. At the initial screening visit more than 80% of subjects were negative to HPV genotypes 6, 11, 16 and 18, found in the qHPV vaccine. This was a higher seronegative rate than seen in a US based study in which only 55.6% were HPV 16 negative and 73.7% HPV 18 negative at baseline, despite being a younger cohort overall (N=99, mean age 21.4 years).⁷⁸ Preliminary data outlined that in our study, 17 % of HIV-positive women had low-grade squamous intraepithelial lesions (LSIL) or greater at screening and 29% had at least one strain of oncogenic HPV present. It was observed that greater numbers of oncogenic HPV types were present in those women with cervical dysplasia.⁷⁹

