Antibody response to HPV types 6, 11, 16 and 18 has been collected and analyzed on over 1500 serology samples for months 0, 7, 12, 18 and 24. Seroconversion rates at month 7 were approximately 93-98% in this HIV-positive population, much higher than anticipated. However, peak Geometric Mean Titres (GMT) were lower than in HIV negative populations. In addition this was associated with a significant decline in antibody levels by month 24, particularly to HPV18. Similar to our findings, Kahn et al., also showed that level of antibody was lower in individuals not on cART in their open label 16-23 year old study of 99 women given the q HPV vaccine.⁸⁰ Of note, we also observed statistically significantly higher levels of incident and persistent infections of vaccine containing types in a short term follow up period. This preliminary data outlines the importance of following this established cohort for long-term immunogenicity. When directly comparing the school based vaccine target age of 9-13 years, the HIV positive girls had a statistically significantly lower peak GMT than age matched HIV comparators.^{81,82} Similar studies conducted by other investigator groups have preliminary data available as well. Weinberg et al, showed that in HIV infected 7-12 year old children, there was a good seroconversion rate at > 94% but noted that the level of antibody to HPV18 was less than for the other genotypes. They also added a fourth dose of the vaccine which demonstrated an appropriate anamnestic response suggesting that should a booster be deemed necessary it should function to appropriately enhance the antibody response.⁸³ A South African based study of the bivalent vaccine demonstrated safety and 100% seroconversion to the vaccine containing serotypes regardless of CD4, HIV viral load and HIV clinical stage of disease.⁸⁴

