5.0 STUDY COHORT

1. Population

Four hundred and seven (407) HIV-positive girls and women (greater than, or equal to, age 11) attending the HIV treatment clinics in each of the 13 sites across Canada and who have enrolled in the original study “A Study of an HPV VLP Vaccine in a Cohort of HIV Positive Girls and Women (CTN 236)” will be offered participation in the study.

Inclusion Criteria

- Enrolled in CTN 236 study
- Able to give fully informed consent or assent

Exclusion Criteria

- Did not receive at least one vaccination via CTN 236, phase 1
- Cannot provide fully informed consent or assent

2. Delays and contraindications to subsequent study procedures

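### Section 16.2 analyses type-specific antibody without regard to month 0 serostatus, so titres and seroresponse can mix vaccine and natural antibody; the effect on waning is undetermined

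*Combined protocol and SAP*

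**What the plan says.** Section 16.0, item 2 (Primary Analysis) states that for each vaccine type "antibody response will be summarized using GMT's calculated for age specific groups within the HIV-positive cohort". It then sets out (a) comparisons with HIV-negative individual data and published GMTs, (b) models of decline from peak, (c) GEE models with an HIV-by-time interaction, adjusted for age, and (d) logistic regression for seroresponse. None of these names an analysis population by baseline serostatus. The covariates in (b) are age, HSV-2, substance use and HIV-related variables. The only HPV-exposure term is the presence and number of HPV strains in (d), which is not serostatus.

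Entry does not narrow the population either. Section 5.0 invites "Four hundred and seven (407) HIV-positive girls and women", and its only vaccine-related exclusion is "Did not receive at least one vaccination via CTN 236, phase 1".

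Section 1.0, item 10 reports that "At the initial screening visit more than 80% of subjects were negative to HPV genotypes 6, 11, 16 and 18"; the next sentence makes clear that this is a seronegative rate. The same item reports "over 1500 serology samples for months 0, 7, 12, 18 and 24", so baseline values exist. Section 12.1.2 defines seropositivity by a titre cutoff for each type, with no requirement for a change from baseline.

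On later doses, section 7.5.7.3 records "antiretroviral therapy, other vaccines" with start and stop dates, but no analysis rule uses that record.

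**The concern.** The primary objective is the antibody response to the vaccine out to 96 months, and the hypothesis is a faster decline with HIV. A participant with natural antibody to a type before dose 1 contributes a titre that is not purely vaccine-induced. If such participants are pooled without distinction, three results are affected:

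- the type-specific GMT can be too high as a measure of vaccine response;
- the HIV-positive to HIV-negative contrast can shift if baseline seropositivity differs between the cohorts;
- the predictors of decline in (b) can be confounded, because prior HPV exposure may go with age, substance use or HIV parameters.

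The seroresponse model in (d) has a separate problem. With a cutoff as the only definition of seropositivity, someone already above it can be classed as a responder whatever the vaccine did. The protocol calls this analysis vital for targeting the vaccine.

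The protocol itself treats baseline status as relevant. The HIV-negative result that it cites is conditional: "100% of the subjects who were antibody negative to the relevant HPV type at baseline had a detectable antibody response at month 7".

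**Working it through.** The plan gives no figure on this point, so there is none to reproduce.

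**Inputs from the documents**
- Cohort 407 (section 5.0).
- Seronegative share above 80% (section 1.0, item 10), so the seropositive share p is below 0.20. Since 0.20 × 407 = 81.4, about 326 or more are seronegative. If the 80% means negative to all four types, p for any one type is smaller.
- Vaccine antibody at month 7 was 10- to 10^4-fold above natural antibody, in HIV-negative data (section 1.0, item 7).
- Seroconversion at month 7 was about 93% to 98% (section 1.0, item 10).

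**Assumptions, not in the documents**
- p from 0.05 to 0.20.
- Seropositive participants have titres R = 2 to 4 times those of seronegative participants.
- The true decline D in seronegative participants is 10-fold.

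**1. GMT level.** Mixed GMT / seronegative GMT = R^p.
- p = 0.05: 2^0.05 = 1.04 and 4^0.05 = 1.07.
- p = 0.20: 2^0.20 = 1.15 and 4^0.20 = 1.32.

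**2. HIV contrast.** With seropositive share q in the HIV-negative cohort and the same R, the ratio is multiplied by R^(p − q). At p = 0.20 and R = 2:
- q = 0.20 gives 1.00;
- q = 0.10 gives 2^0.10 = 1.07;
- q = 0 gives 1.15.

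The documents do not give q.

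**3. Waning on the log scale.** Observed fold decline = D / (R_late / R_peak)^p. At p = 0.20:
- constant R: 10.0-fold, no bias;
- R rising from 1 to 2: 10 / 2^0.20 = 8.7-fold, understated;
- R falling from 3 to 1.5: 10 / 0.5^0.20 = 11.5-fold, overstated.

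**4. The protocol's own natural-antibody figure.** Suppose natural antibody is stable and simply adds to vaccine antibody, with p = 0.20.
- At one-tenth of the vaccine peak: R_peak = 1.1 and R_late = (0.1 + 0.1) / 0.1 = 2. The GMT inflation is 1.1^0.20 = 1.02 at peak and 1.15 late, and the decline reads 10 / (2 / 1.1)^0.20 = 8.9-fold.
- At one-hundredth: R goes from 1.01 to 1.1, and the decline reads 9.8-fold.
- At 10^-4 it stays essentially 10.0-fold.

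**5. Raw scale.** Section 16.2(c) specifies a unity link and does not say that titres are log-transformed. Take seronegative means of 100 at peak and 10 late, a drop of 90. At p = 0.20:
- constant R = 2 gives 120 − 12 = 108, overstated;
- R rising from 1 to 2 gives 100 − 12 = 88.

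**6. Seroresponse in (d).** Assume that all 407 are assessed, that 2% to 7% are true non-responders whatever their baseline status, and that baseline seropositives stay above the cutoff.
- True non-responders: 0.02 × 407 = 8 to 0.07 × 407 = 28.
- Counted as responders at p = 0.20: 0.20 × 8 = 1.6 to 0.20 × 28 = 5.6, so about 2 to 6.
- At p = 0.05: 0.4 to 1.4.

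**7. Doses outside the CTN 236 regimen.** Such a dose would raise later titres. The protocol says of another group's study: "They also added a fourth dose of the vaccine which demonstrated an appropriate anamnestic response". It gives neither the size of that response nor any frequency in this cohort, so no size is computed.

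**The case against.** The best defence has several parts.

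- **The plan is silent; it does not choose to pool.** This is fair. Run as written, however, every vaccinated participant enters. The Rationale in section 4.0 refers to known confounders, but 16.2(c) names only age, and (b) and (d) compare within the HIV-positive cohort.
- **An all-vaccinated analysis is legitimate in a cohort study of effectiveness.** This stands. It is why seronegative results belong alongside it rather than in place of it.
- **The individual-level comparison in (a) is by age group, 9-13 and 16-26.** Section 7.2.1 describes HIV in young girls as mainly perinatally acquired. The cohort-wide 20% may therefore be too high for the youngest group. This stands as a limit on size.
- **Seroresponse is not defined in (d), and the background speaks of seroconversion.** This is true, but the only definition in the document is the cutoff, so the problem is open rather than excluded.

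A reader might infer that waning is understated, or that a true HIV-positive to HIV-negative ratio of 0.70 would read as 0.80 to 0.92 (0.70 × 1.15 and 0.70 × 1.32). The documents support neither. Steps 3 and 5 show that the bias in waning can be nil or of either sign. The ratios require no seropositives in the comparator cohort, and its share is not given.

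A reader might also infer that booster doses are distorting late titres. No passage shows that any participant received one. Nor do the documents show that the published GMTs used for women over 26 come from type-naive populations; the cited baseline-negative result is a month 7 response rate.

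**Conclusion.** The gap is real and lies in the primary analysis: a baseline value already held, and directly relevant to a type-specific titre, is used nowhere in 16.2 (a) to (d). The inflation of the group GMT is 1.04 to 1.32 if 5% to 20% are seropositive with 2- to 4-fold higher titres. If natural antibody is additive and follows the protocol's own figures, it is 1.02 or less at peak and at most 1.15 after a 10-fold decline. The HIV contrast is biased only so far as seropositive shares, or their excess, differ between cohorts.

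The size and direction of the effect on waning cannot be settled from the documents. In (d), up to about one-fifth of true non-responders could be counted as responders, under the assumptions in step 6.

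Extra HPV vaccine doses are a secondary point. The direction would be clear (waning hidden), but whether any occurred is unknown. Overall this is a change that should be made, not a flaw that invalidates the study.

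**What to change.** - **Models (b) to (d), HIV-positive cohort.** Add month 0 type-specific serostatus as a covariate. In the GEE, include its interaction with time, since a main effect alone allows only a constant offset. State that titres are log-transformed.
- **GMTs and waning.** Report them in participants seronegative to that type at month 0 alongside all vaccinated participants. Apply the same rule to the HIV-negative data where baseline serology is available. State the serostatus of the population behind each published GMT used.
- **Seroresponse in (d).** Define it as conversion from seronegative for that type. The serostatus covariate then matters only in a supportive analysis of all participants.
- **Extra doses.** Run a sensitivity analysis excluding titres drawn after any HPV vaccine dose outside the CTN 236 regimen, using the dates recorded under 7.5.7.3.

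A further condition on baseline HPV DNA is best avoided in the main analysis. Girls who are pre-menarchal and not sexually active have no genital sampling (section 5.2.1), so the condition would apply unevenly.

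**Cost.** For the HIV-positive cohort this is analysis wording, because the data exist. Someone must confirm that the comparator cohort has baseline serology. The seronegative analysis loses up to about 20% of participants per type, about 81 of 407 at most.
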